10.8 Evaluating AEs and SAEs

10.8.1 Assessment of Intensity

The Investigator will make an assessment of intensity for each AE and SAE reported during the study. The assessment will be based on the Investigator's clinical judgment. The intensity of each AE and SAE recorded in the eCRF should be assigned to one of the following three categories:

Mild:

An event that is easily tolerated by the participant, causing minimal discomfort and not interfering with everyday activities.

Moderate:

An event that is sufficiently discomforting to interfere with normal everyday activities.

Severe:

An event that prevents normal everyday activities.

An AE that is assessed as severe should not be confused with an SAE. Severity is a category utilized for rating the intensity of an event; and both AEs and SAEs can be assessed as severe. An event is defined as 'serious' when it meets one of the pre-defined outcomes as described in Section 10.2 Definition of Serious Adverse Event.

10.8.2 Assessment of Causality

The Investigator is obligated to assess the relationship between IMP and the occurrence of each AE/SAE. The Investigator will use clinical judgment to determine the relationship. Alternative causes such as natural history of the underlying diseases, concomitant therapy, other risk factors, and the temporal

relationship of the event to the IMP will be considered and investigated. The Investigator will also consult the Investigator's Brochure in the determination of his/her assessment.

All AEs will be assessed by the Principal Investigator or qualified and authorized delegate as to whether there is a 'reasonable possibility that the drug caused the event' and on that basis be classified as either 'related' or 'not related'.

There may be situations when a SAE has occurred and the Investigator has minimal information to include in the initial report to the Sponsor. However, it is very important that the Investigator always make an assessment of causality for every event prior to transmission of the SAE form to the Sponsor. The Investigator may change his/her opinion of causality in light of follow-up information, amending the SAE form accordingly.

10.8.3 Follow-up of AEs and SAEs

the situation.

After the initial AE/SAE report, the Investigator is required to proactively follow each participant and provide further information to the Sponsor on the participant's condition.

All AEs and SAEs documented at a previous visit/contact and are designated as ongoing, will be reviewed at subsequent visits/contacts.

All AEs will be followed until resolution, until the condition stabilizes, or until 30 days after the participant's Visit 17 Follow Up, whichever occurs first. At which time, the appropriate AE/SAE eCRF page(s) will be updated. SAEs and renal AEs that are ongoing at the Follow-up visit (Visit 17) will be followed until resolution, stabilization of participant condition, or study end, whichever occurs first. In such cases, follow-up Serious Adverse Event Report (SAER) forms will be completed at the Follow-up visit (Visit 17) as well as completed upon resolution, stabilization, or study end, whichever occurs first. "Study end" is when all participants have completed the study.

The Investigator will ensure that follow-up includes any supplemental investigations as may be indicated to elucidate the nature and/or causality of the AE or SAE. This may include additional laboratory tests or investigations, histopathological examinations, or consultation with other health care professionals.

The Sponsor may request that the Investigator perform or arrange for the conduct of supplemental measurements and/or evaluations to elucidate as fully as possible the nature and/or causality of the AE or SAE. The Investigator is obligated to assist. If a participant dies during the study or during a recognized follow-up period, the Sponsor will be provided with a copy of the death certificate and any post-mortem findings, including histopathology.

New or updated information will be recorded on the originally completed SAE with all changes signed and dated by the Investigator. The updated SAE form should be re-sent to the Sponsor within the time frames outlined below in Section 10.8 Prompt Reporting of the SAEs to the Sponsor.

[figure not shown]
Any clinical adverse event that is serious (as defined above in Section 10.2)

occurring during the course of the study, irrespective of the treatment received by the participant, must be reported to the Sponsor and Sponsor's agent within 24 hrs (or sooner if possible) of the Investigator or designee becoming aware of

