9.4.5 Early Discontinuation

Investigational Medicinal Product administration may be stopped early if an AE, tolerability issue or inter-current illness occurs that in the opinion of the Investigator (or designee) necessitates cessation of the IMP. Study drug administration must be ceased for all SAEs considered related to the experimental medication.

Note that early cessation of IMP does not necessarily mean the participant is withdrawn from the study. With any early cessation, all evaluations and tests scheduled during the study must be conducted if possible.

- Requests early discontinuation.
- requires treatment with an excluded medication, as defined in Exclusion Criteria (Section 8.2).
- at any point in the study, a participant becomes ill with symptoms of/or tests positive for COVID-19 infection.
- has a positive pregnancy test or becomes pregnant.
- in the Investigator's opinion, the participant is experiencing a clinically significant deterioration in his or her clinical state.
- experiences a Serious Adverse Event deemed to be related to the IMP.
- experiences a severe adverse event deemed to be related to the IMP.
- has an increase in post-enrollment QTcF interval as defined below (see also Section 9.5.8).

Investigational Medicinal Product must be discontinued at any time during the study in the event any of the following are observed post-enrollment:

QTcF Criteria

- A post-enrollment QTcF duration of ≥ 500 ms confirmed by repeat continuous ECG.
- A clinically significant increase of ≥ 60 ms (confirmed by repeat continuous ECG) compared to the average QTcF interval at Baseline (before dosing) is observed.

Participants who have received IMP for longer than 2 weeks and discontinue prematurely any time after Visit 5 should return to the investigational site for final safety and efficacy assessments as scheduled for the EOT visit (Week 13, Visit 16) and complete the study exit form.

Participants who discontinue from the trial prior to receiving any treatment or who discontinue after having received treatment only up to Visit 5 (Week 2 post-baseline) may be replaced.

Participants with early treatment cessation due to SAEs must be followed-up and provided appropriate medical care until their signs and symptoms have remitted or stabilized, or for the remaining study period (until study end), whichever comes sooner. "Study end" is when all participants have completed the study.

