10.1 Definition of Adverse Event

An adverse event is any untoward medical occurrence associated with the use of a drug in humans, whether or not considered drug related. An AE can be any unfavorable and unintended sign (e.g., an abnormal laboratory finding), symptom or disease temporally associated with the use of a drug, without any judgment about causality.

AEs can include the following:

- Exacerbation of a chronic or intermittent pre-existing condition including either an increase in frequency and/or intensity of the condition.
- Conditions detected or diagnosed after IMP administration even though it may have been present prior to the start of the study.
- Signs, symptoms, or the clinical sequelae of a suspected interaction.
- Signs, symptoms, or the clinical sequelae of a suspected overdose of either IMP or a concurrent medication.

SAEs are a sub-category of AEs that are defined in Section 10.2, below. AEs/SAEs are recorded and reported from the time of first dose of IMP until Follow-up (Visit 17).

Planned hospital admissions for an illness or a disease that existed prior to administration of IMP or enrollment in the clinical study are generally not to be considered AEs. Individuals who have planned surgical procedures that would occur during the study are to be excluded from the study (Exclusion 43). If the participant has a planned hospital admission (non-surgical), the Investigator should consult with the Medical Monitor to ensure this will not cause disruption of IP administration or would not qualify the participant for exclusion.

Note that medical or surgical procedures are not considered AEs (e.g., endoscopy); however, the condition that leads to the procedure is an AE.

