10.9.0 Completion and transmission of the SAE reports

Serious Adverse Events will be processed by the Pharmacovigilance Team at support of and review by the Medical Monitor and Neuren's Medical Team.

with the

A serious adverse event report (SAER) form is to be completed for each SAE occurring up to the final study visit, regardless of causality. This includes renal AEs that meet criteria for an SAE. In addition, the SAE is to be recorded on the appropriate section of the eCRF. The SAER must be submitted to the Pharmacovigilance Team at the email below within 24 hours of the time the SAE is first observed.

| Submit SAER form via email within 24 hours of |
|--|
| the event to: |
| - The state of the |

The Medical Monitor or pharmacovigilance department will contact the Investigator should it be necessary to clarify any of the event information. The Investigator should provide follow-up information for the event to the Medical Monitor or pharmacovigilance department as soon as it becomes available. If required, the Investigator should report these events to the local IRB.

The SAE form will always be completed as thoroughly as possible with all available details of the event and signed by the Investigator (or authorized designee). If the Investigator does not have all information regarding an SAE, he/she will not wait to receive additional information before notifying the Medical Monitor of the event and completing the form. The form will be updated when additional information is received.

The Investigator will always provide an assessment of causality at the time of the initial report as described in Section 10.7.2 Assessment of Causality.

Any event that, in the opinion of the Principal Investigator, may be of immediate or potential concern for the participant's health or well-being will be reported to the Medical Monitor.

In accordance with applicable regulations and local laws, the Sponsor will identify and report within the required time frame to regulatory authorities and Investigators all adverse events assessed as related that are determined to be both serious and unexpected (Suspected Unexpected Serious Adverse Events reporting SUSAR). Investigators will be responsible for reporting this safety information to their IRB.

[figure not shown]

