SAEs that are ongoing at the Follow-up visit (Visit 17) will be followed until resolution, stabilization of participant condition, or study end, whichever occurs first. In such cases, follow-up SAER forms will be

completed at the Follow-up visit (Visit 17) as well as completed upon resolution, stabilization, or study end, whichever occurs first. "Study end" is when all participants have completed the study.

All SAE and AE data will be reviewed by the DSMC at scheduled meetings.

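### SAE follow-up is limited to study end with no minimum, so a late finisher's unresolved SAE may have a shorter required window than the 30 days given to AEs in general

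*Protocol*

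**What the plan says.** Protocol 10.8.3 contains two follow-up limits.

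- The general rule: "All AEs will be followed until resolution, until the condition stabilizes, or until 30 days after" the child's own Visit 17, whichever comes first. The sentence after it reads "At which time, the appropriate AE/SAE eCRF page(s) will be updated", so it has SAEs in view as well. Section 10.1 also states that "SAEs are a sub-category of AEs".
- The specific rule: SAEs and renal AEs still ongoing at Visit 17 "will be followed until resolution, stabilization of participant condition, or study end, whichever occurs first". Study end "is when all participants have completed the study", so it is a date for the whole trial and not for the child.

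No wording joins the two sentences as an exception or says that the later date applies, and the specific rule has no minimum number of days.

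Two other sections give only the study-end limit for SAEs. Section 10.9.0 restates it for SAEs open at Visit 17. Section 9.4.5, on treatment stopped because of an SAE, requires follow-up and medical care until signs and symptoms have remitted or stabilized "or for the remaining study period (until study end), whichever comes sooner".

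**The concern.** A separate sentence for serious events is normally there to lengthen their follow-up. Here it does so for children who finish early, because study end is then far off. For children who finish near the end of the trial it can do the reverse: the required window for an unresolved SAE shrinks with the time left in the trial, while a non-serious, non-renal AE keeps its 30 days.

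The form rule in 10.8.3 shows the same thing. A follow-up report is due at Visit 17 and another at resolution, stabilization or study end. For the last finisher, if completion means Visit 17, Visit 17 and study end are the same date, so the second report adds no follow-up.

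What is at stake is the outcome information, and under 9.4.5 the care, for a serious event still open at a child's last visit. Safety is a primary objective of this pediatric study.

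**Working it through.** The plan gives no figure of its own to reproduce. The check is date arithmetic.

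**Inputs**

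- General AE limit: 30 days after the child's own Visit 17 (10.8.3).
- SAE limit: study end (10.8.3, 10.9.0, 9.4.5).
- Study end is taken as the last child's Visit 17. This is an assumption. Section 7.4 runs the study duration to the Week 15 follow-up and 9.2.17 places the exit form there, but neither defines completion.
- D = days from a child's Visit 17 to the last child's Visit 17.
- Last dose no later than Day 91 (9.4.2). Visit 17 at Week 15, +4 days, which is Day 105 to 109.

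**Required SAE window after Visit 17**

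- If the SAE sentence governs: window = D, shortfall against other AEs = max(0, 30 - D).
- If both sentences are duties to be met together: window = max(30, D), shortfall = 0.

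| D (days) | SAE sentence governs | Cumulative duties | Shortfall if SAE sentence governs |
|---|---|---|---|
| 0 (last finisher) | 0 | 30 | 30 |
| 7 | 7 | 30 | 23 |
| 14 | 14 | 30 | 16 |
| 21 | 21 | 30 | 9 |
| 28 | 28 | 30 | 2 |
| 30 | 30 | 30 | 0 |
| 60 | 60 | 60 | 0 |
| 180 | 180 | 180 | 0 |

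**Worst case counted from the last dose.** For the last finisher dosed to Day 91, Visit 17 falls 105 - 91 = 14 to 109 - 91 = 18 days after the last dose. If the SAE sentence governs, required SAE follow-up stops there. Another AE could be followed to 14 + 30 = 44 to 18 + 30 = 48 days.

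**Who can be affected.** The staggered enrollment protects the first three Group 1 children. Group 3 cannot start until two successive two-week periods have passed, 14 + 14 = 28 days, so on nominal visit dates their shortfall is at most 30 - 28 = 2 days. If each of the two DSMC reviews takes one week (assumed), the gap is 28 + 14 = 42 days and the shortfall is zero.

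The documents give no accrual period. As an illustration only, assume evenly spaced completions over 6 to 24 months:

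- 10 children: spacing is 6 × 30.4375 / 9 = 20.3 days at 6 months (2 children with D below 30) and 81.2 days at 24 months (1 child).
- 20 children: spacing is 6 × 30.4375 / 19 = 9.6 days at 6 months (4 children) and 38.4 days at 24 months (1 child).

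That is 1 to 2 of 10 or 1 to 4 of 20, always including the last finisher. The window matters for such a child only if an SAE is neither resolved nor stable at Visit 17. The documents support no rate for that.

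**The case against.** The strongest reply is that nothing conflicts. Both sentences impose a duty to follow, SAEs fall under both, and neither releases an SAE from the other. A site that follows to the later date satisfies both, and the window is then never below 30 days. This is a fair reading. A reader might infer that a site cannot tell when required follow-up ends; that goes too far, because the later date always complies. The reply does not fully cure the text, however. Sections 10.9.0 and 9.4.5 give study end alone, and a site working from them would stop there.

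Other replies also carry weight.

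- Completion is undefined. If it included the 30-day AE follow-up, the shortfall would vanish for every D. No text says that it does, and 7.4 and 9.2.17 point to Visit 17.
- The 14 to 18 against 44 to 48 day comparison is an extreme. Under 9.4.5 a related SAE stops treatment, and scheduled evaluations then continue if possible, so an SAE arising mid-treatment is observed off drug for much longer. The comparison fits unrelated SAEs, or those arising close to the end of treatment.
- Other duties have no end date. Under 10.8.3 "the Investigator is required to proactively follow each participant and provide further information to the Sponsor", and the sponsor may ask for further evaluations, with which the investigator must help. Under 10.9.0, "The form will be updated when additional information is received". These soften the effect but set no date until which contact is required.
- Renal follow-up may be governed by sections not in this copy (9.5.2.1 to 9.5.2.3, 10.3, 10.11). The renal part of this point therefore rests on the one sentence in 10.8.3.

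**Conclusion.** The point stands at low severity. It depends on two conditions: that the SAE sentence governs, as 10.9.0 and 9.4.5 suggest, and that completing the study means Visit 17. Under both, a child finishing less than 30 days before the last child has a required SAE window shorter than that for other AEs, and the last finisher has none. If the sentences are cumulative, nothing is lost and only the wording needs settling.

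Three stronger inferences are not supported.

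- That SAEs in general get less follow-up than other AEs: when the SAE sentence governs, a child with D above 30 gets more.
- That safety results would change: AE incidence is counted to the last study visit (Protocol 6.3.1.1; SAP 7.2), so the follow-up limit alters no incidence summary.
- That enrolled children lost follow-up because of this text: SAP 2.2 reports that nobody was enrolled under protocol version 3.0, the version in hand, and the wording of the other versions is not visible.

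**What to change.** In 10.8.3, 10.9.0 and 9.4.5, replace study end as the SAE follow-up limit with the later of study end and 30 days after the child's Visit 17, or after the last study visit if Visit 17 is not done. Apply the same wording to renal AEs in the 10.8.3 sentence, subject to the renal sections not in this copy. A clause saying that the general 30-day limit applies to AEs other than SAEs and renal AEs would remove the overlap.

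The SAE window becomes max(30, D). The last finisher goes from 0 to 30 days, a child with D = 14 goes from 14 to 30, and no child's window shortens. The cost is about one line in each of three sections, and up to 30 more days of contact for the few late finishers with an unresolved event. The general AE rule already allows follow-up to 30 days past the last child's Visit 17, so the latest possible follow-up date does not move.

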10.9 Prompt Reporting of the SAEs to the Sponsor

Once an Investigator or delegate becomes aware that an SAE has occurred in a study participant, she/ he will report the information to the Sponsor's appointed agent within 24 hrs.

10.9.0 Completion and transmission of the SAE reports

Serious Adverse Events will be processed by the Pharmacovigilance Team at support of and review by the Medical Monitor and Neuren's Medical Team.

with the

A serious adverse event report (SAER) form is to be completed for each SAE occurring up to the final study visit, regardless of causality. This includes renal AEs that meet criteria for an SAE. In addition, the SAE is to be recorded on the appropriate section of the eCRF. The SAER must be submitted to the Pharmacovigilance Team at the email below within 24 hours of the time the SAE is first observed.

| Submit SAER form via email within 24 hours of |
|--|
| the event to: |
| - The state of the |

The Medical Monitor or pharmacovigilance department will contact the Investigator should it be necessary to clarify any of the event information. The Investigator should provide follow-up information for the event to the Medical Monitor or pharmacovigilance department as soon as it becomes available. If required, the Investigator should report these events to the local IRB.

The SAE form will always be completed as thoroughly as possible with all available details of the event and signed by the Investigator (or authorized designee). If the Investigator does not have all information regarding an SAE, he/she will not wait to receive additional information before notifying the Medical Monitor of the event and completing the form. The form will be updated when additional information is received.

The Investigator will always provide an assessment of causality at the time of the initial report as described in Section 10.7.2 Assessment of Causality.

Any event that, in the opinion of the Principal Investigator, may be of immediate or potential concern for the participant's health or well-being will be reported to the Medical Monitor.

In accordance with applicable regulations and local laws, the Sponsor will identify and report within the required time frame to regulatory authorities and Investigators all adverse events assessed as related that are determined to be both serious and unexpected (Suspected Unexpected Serious Adverse Events reporting SUSAR). Investigators will be responsible for reporting this safety information to their IRB.

[figure not shown]
SAEs that are ongoing at the Follow-up visit (Visit 17) will be followed until resolution, stabilization of participant condition, or study end, whichever occurs first. In such cases, follow-up SAER forms will be

completed at the Follow-up visit (Visit 17) as well as completed upon resolution, stabilization, or study end, whichever occurs first. "Study end" is when all participants have completed the study.

All SAE and AE data will be reviewed by the DSMC at scheduled meetings.

10.10 Deaths

A SAER form is to be competed for all deaths. Death will be recorded in the eCRF. Source documentation (e.g., autopsy report, death certificate) to confirm the cause of death will be reviewed by the DSMC.

10.12 Pregnancy

Pregnant, lactating, or breastfeeding females are to be excluded from this study. In the event of pregnancy, it will be reported on a pregnancy form, and will be followed up to determine outcome, including spontaneous or voluntary termination, details of birth, and the presence or absence of any birth defects or congenital abnormalities. The investigator should report all pregnancies in female clinical trial participants to the Premier Pharmacovigilance Team as soon as possible using the Pregnancy Data Collection Form.

Submit Pregnancy Data Collection form vial email to:

It is not expected that there will be sexually active participants in the study population, and as such some of the provisions that follow may have limited applicability based on the age range of study participants and the nature of the disease under study. These provisions are nonetheless included for purposes of completeness.

Participants of childbearing potential must abstain from sexual activity for the duration of the study and for at least 30 days thereafter. If a participant is sexually active or becomes sexually active during the study, she or he must use 2 clinically acceptable methods of contraception (e.g., oral, intrauterine device [IUD], diaphragm plus spermicide, injectable, transdermal or implantable contraception, condom use (male type only)) for the duration of the study and for at least 30 days thereafter.

